# **PROTOCOL SYNOPSIS**

#### TITLE

A Phase 2 Proof-of-concept Study to Evaluate the Efficacy and Safety of MEDI3902 in Mechanically Ventilated Patients for the Prevention of Nosocomial Pneumonia Caused by Pseudomonas aeruginosa

#### HYPOTHESES

[figure not shown]
Prophylactic use of MEDI3902 in mechanically ventilated subjects in the intensive care unit (ICU) who are colonised with *Pseudomonas aeruginosa* (*P aeruginosa*) in the lower respiratory tract will reduce the incidence of nosocomial pneumonia caused by *P aeruginosa* through 21 days postdose irrespective of mechanical ventilation status at time of diagnosis.

A single intravenous (IV) dose of MEDI3902 administered to mechanically ventilated subjects in the ICU will have an acceptable safety profile.

#### TARGET SUBJECT POPULATION

Subjects in this study will be adult patients 18 years of age or older in the ICU, who require mechanical ventilation and who are currently free of *P aeruginosa*-related disease, but are colonised with *P aeruginosa* in the lower respiratory tract.

#### INVESTIGATIONAL PRODUCT, DOSAGE, AND MODE OF ADMINISTRATION

At the study start, subjects were to be randomly assigned to receive a single dose of the mg MEDI3902, mg MEDI3902, or placebo administered via IV infusion on Day 1. Subsequent to Amendment 2, subjects will be randomly assigned to receive a single dose of the mg MEDI3902 (or in the case of dose adjustment, mg MEDI3902) or placebo administered via IV infusion on Day 1.

#### Primary Analysis

The percent reduction of incidence of nosocomial pneumonia caused by *P aeruginosa* through 21 days postdose will be the primary efficacy endpoint. For subjects with multiple *P aeruginosa* pneumonia events, only the first occurrence will be used in the primary analysis. Subjects with mixed cultured results, which include *P aeruginosa*, will be counted towards the primary endpoint.

The primary analysis of the primary endpoint will be evaluated using the mITT Population. *P aeruginosa* pneumonia that occurs prior to discontinuation will contribute to the primary efficacy analysis. If no *P aeruginosa* pneumonia occurs prior to discontinuation, the subject will be considered as having no *P aeruginosa* pneumonia infection in the primary efficacy analysis. A Poisson regression model with robust variance (Zou, 2004) will be used as the primary efficacy analysis, to estimate the relative risk of *P aeruginosa* pneumonia through 21 days postdose between the **Reput** mg MEDI3902 and placebo groups, using the term of treatment group as a covariate. The relative risk reduction, defined as 1 – Relative Risk (RR), and its corresponding 2-sided 90% CI will be estimated from the model. In addition, the 2-sided p-value testing the null hypothesis that the incidence of having *P aeruginosa* pneumonia between the **Reput** mg MEDI3902 and placebo groups are the same will also be obtained from the model. The significance testing will be performed against a 2-sided alpha level of 0.2.

The Poisson regression with robust variance analysis will be implemented using the SAS PROC GENMOD procedure with the REPEATED statement for subject ID and logarithm link. The estimated parameter  $\hat{\beta}$  [ie, log  $(\widehat{RR})$ ], 2-sided 80% confidence interval for  $\hat{\beta}$ , and the 2-sided p-value will be provided from the SAS outputs. The estimated relative risk  $(\widehat{RR})$  and corresponding confidence interval for the relative risk is given by exponentiating  $\hat{\beta}$  and its confidence limits. Therefore, the percent of relative risk reduction is given by [(1 – exp  $(\hat{\beta})$ ) \* 100%]. The confidence interval for the percent of relative risk reduction is given by ([1 – exp (upper confidence limit for  $\hat{\beta}$ ) \* 100%], [1 – exp (lower confidence limit for  $\hat{\beta}$ ) \* 100%]).

Sample Size/Power Calculation

Approximately 286 colonised subjects will be enrolled and randomised (1:1 ratio) to  $\frac{\text{Red}}{\text{r}}$  mg MEDI3902 (or in the case of dose adjustment,  $\frac{\text{Red}}{\text{r}}$  mg MEDI3902; n = 143) or placebo (n = 143).

Key assumptions used for sample size/power calculations: placebo group *P aeruginosa* pneumonia incidence 20%, relative reduction 50%, at least 80% power, 20% adjustment for attrition. Relative reduction of 50% was recommended to Sponsor as a clinically meaningful effect by experts in critical care, pulmonary medicine, and infectious diseases. In addition, 50% relative reduction was demonstrated in a study by Francois and colleagues (Francois et al, 2012) involving a monoclonal antibody to prevent *Pseudomonas* pneumonia in mechanically ventilated patients, supporting the biological feasibility of such an effect.

Power calculations are based on Poisson regression with robust variance comparing each MEDI3902 treatment group separately versus placebo, 2-sided, with  $\alpha = 0.2$ .

The sample size may be modified after approximately 50% of the subjects are enrolled and followed through 21 days postdose based on blinded assessment of the event rate and/or attrition rate in the overall population.

# LIST OF ABBREVIATIONS

Abbreviation or Specialized Term	Definition
ADA	anti-drug antibody
AE	adverse event
AESI	adverse event of special interest
ALP	Alkaline phosphatase
ALT	alanine transaminase
APACHE-II	Acute Physiology and Chronic Health Evaluation-II
AST	aspartate transaminase
AUC	area under concentration time curve
AUC∞	area under the concentration-time curve from time zero to infinity
AUC Day22-Day29	area under concentration time curve from day 22 to day 29
BAL	bronchoalveolar lavage
CCC	Clinical Coordinating Centre
C max	mean observed maximum concentration
CPIS	Clinical Pulmonary Infection Score
CRP	C-reactive protein
DMC	data monitoring committee
EC 90	effective serum concentration associated with 90% survival
eCRF	electronic case report form
EDC	electronic data capture
EQ-5D-5L	EuroQol - 5 Dimensions - 5 Levels
FAAN	Food, Allergy and Anaphylaxis Network
FiO 2	fraction of inspired oxygen
GLP	Good Laboratory Practice
GMP	Good Manufacturing Practice
HIV	human immunodeficiency virus
HL	Hy's Law
ICF	informed consent form
ICH	International Council for Harmonisation
ICU	intensive care unit
IEC	Independent Ethics Committee
Ig	immunoglobulin
IgG1	immunoglobulin G1
IL	interleukin
IRB	Institutional Review Board
ITT	intent-to-treat
IV	intravenous
IWRS	interactive web response system
LLOQ	lower limit of quantification

Abbreviation or Specialized Term	Definition
mAb	monoclonal antibody
mITT	modified intent-to-treat
MMP-9	matrix metalloproteinase 9
MPO	myeloperoxidase
NE	neutrophil elastase
NIAID	National Institute of Allergy and Infectious Diseases
NOAEL	no observed adverse effect level
O 2	oxygen
ОРК	opsonophagocytic killing
P aeruginosa	Pseudomonas aeruginosa
PaO 2	partial pressure of oxygen
PCR	polymerase chain reaction
PD	pharmacodynamic
РК	pharmacokinetics
PSB	protected-specimen brush
RBC	red blood cell
SAE	serious adverse event
SAP	statistical analysis plan
SID	subject identification
SOFA	Sequential Organ Failure Assessment
TEAE	treatment-emergent adverse event
TESAE	treatment-emergent serious adverse event
ΤΝFα	tumour necrosis factor alpha
ULN	upper limit of normal
VAP	ventilator-associated pneumonia
Vd ss	volume of distribution at steady state
WBC	white blood cell
w/v	weight/volume

# **1 INTRODUCTION**

# 1.1 Disease Background

*Pseudomonas aeruginosa (P aeruginosa)* is an important nosocomial pathogen, and pneumonia is one of its most important manifestations. Mechanical ventilation is the most important risk factor for nosocomial pneumonia caused by *P aeruginosa*, with cumulative risk increasing with the duration of ventilation (Zahar et al, 2009). In one study, *P aeruginosa* accounted for 13% of cases of microbiologically confirmed pneumonia acquired in the intensive care unit (ICU) by patients who were not mechanically ventilated, and 24% of cases in those who were (Esperatti et al, 2010). In a review of global epidemiology data, *P aeruginosa* caused approximately 27% of ventilator-associated pneumonia (VAP; Jones, 2010). Respiratory tract colonisation with *P aeruginosa* is another important risk factor (Rehm and Kollef, 2014). Despite the existence of antipseudomonal antibiotics, pneumonia, particularly VAP, due to *P aeruginosa* remains associated with significant mortality and morbidity, increased ICU and hospital length of stay, and substantial economic burden. Although general strategies exist to decrease the incidence of pneumonia in mechanically ventilated patients, there are no systemic agents approved for the prevention of pneumonia caused by *P aeruginosa*.

# 1.2 MEDI3902 Background

[figure not shown]
MEDI3902 is briefly described below. Refer to the current Investigator's Brochure for details.

*P aeruginosa* possesses a number of virulence factors that play a role in the severity of disease, and MEDI3902 was developed to target two of these factors. Reducted

Re dao	
ted	
Redacted	
Redacted	

# 1.4 Summary of Clinical Experience

Redacted	

# 1.5 Rationale for Conducting the Study

Patients in the ICU are at risk for developing serious pneumonia infection and mechanical ventilation increases the risk for pneumonia in the ICU. *P aeruginosa* is a common cause of ICU pneumonia and multidrug resistance has complicated the management of *P aeruginosa* infection. Even when not antibiotic resistant, *P aeruginosa* is an important nosocomial pathogen associated with high morbidity and mortality (Kollef et al, 2014). With limited antimicrobial therapeutic options, consideration of new approaches, such as immunoprophylaxis for the prevention of *P aeruginosa* would address an important unmet need.

The efficacy of MEDI3902 for the prevention of lethal *P aeruginosa* pneumonia was demonstrated in animal models. Prophylactic use of MEDI3902 is anticipated to prevent *P aeruginosa*-related disease in at-risk patients in the ICU. It is being developed for the prevention of nosocomial pneumonia in high-risk patients who are likely to be mechanically ventilated with the expectation that they will require ventilation for  $\geq$  72 hours and who also have lower respiratory tract colonisation with *P aeruginosa*.

MEDI3902 was found to be generally safe in the initial Phase 1 study. Because there is no correlate of protection for *P aeruginosa* disease, the next development step is to evaluate if

the PK and PD profile translate into clinical efficacy and evaluate the safety profile in the target population.

The current study is designed to determine the efficacy, safety, and PK responses to MEDI3902 in adult subjects admitted to the ICU who require mechanical ventilation and who are also colonised with *P aeruginosa* in the lower respiratory tract. Results will also form the basis for subsequent studies in adult populations at high risk for *P aeruginosa* disease.

# 1.6 Research Hypotheses

Prophylactic use of MEDI3902 in mechanically ventilated subjects in the ICU who are colonised with *P aeruginosa* in the lower respiratory tract will reduce the incidence of nosocomial pneumonia caused by *P aeruginosa* through 21 days postdose irrespective of mechanical ventilation status at time of diagnosis.

A single IV dose of MEDI3902 administered to mechanically ventilated subjects in the ICU will have an acceptable safety profile.

# 2 OBJECTIVES

# 2.1 Objectives

[figure not shown]
# 2.1.1 Primary Objective

- 1. To evaluate the effect of MEDI3902 in reducing the incidence of nosocomial pneumonia caused by *P aeruginosa*
- 2. To evaluate the safety of a single IV dose of MEDI3902 in mechanically ventilated patients

#### 2.1.2 Secondary Objectives

- 1. To evaluate the serum PK of MEDI3902
- 2. To evaluate the serum ADA responses to MEDI3902

Reda cted				

# 2.2 Study Endpoints

#### 2.2.1 Primary Endpoint

Efficacy of MEDI3902:

1. Incidence of nosocomial pneumonia caused by P aeruginosa through 21 days postdose

Safety of MEDI3902:

1. Treatment-emergent AEs (TEAEs), treatment-emergent SAEs (TESAEs) and AESIs through 49 days postdose

#### 2.2.2 Secondary Endpoints

- 1. MEDI3902 serum concentration and PK parameters through 49 days postdose
- 2. MEDI3902 ADA response in serum through 49 days postdose

Reda cted		

Redacted	
	_ Redacted
Redacted	

# 3 STUDY DESIGN

# 3.1 Description of the Study

#### 3.1.1 Overview

This is a Phase 2, randomised, double-blind, placebo-controlled, single-dose, dose-ranging, proof-of-concept study evaluating 2 dosage levels of MEDI3902 in mechanically ventilated patients in the ICU who are at high risk for *P aeruginosa* infections and who are currently free of *P aeruginosa*-related disease but are colonised with *P aeruginosa* in the lower respiratory tract. At study start, approximately 429 subjects were to be enrolled and dosed at approximately 120 sites primarily in Europe. Subjects were to be randomly assigned in a 1:1:1 ratio to receive a single IV dose of the mathematical mathemati

However, based on data from a separate study in a similar population with another monoclonal antibody, data from a PK study in mice (see Section 3.2.1) and from simulation results using data from the Phase 1 study (Study D5470C00002), a single dose of 500 mg MEDI3902 is not expected to maintain the target level of  $\mu$ g/mL for 21 days. Therefore, enrolment in the target mg MEDI3902 group will be discontinued. Approximately 286 subjects will be randomised in a 1:1 ratio to one of 2 treatment groups.

A PK interim analysis will be performed after at least 10 subjects in each of the **body** mg MEDI3902 and placebo groups are followed through 21 days postdose. The interim PK analysis will allow the determination of serum PK profile of MEDI3902 in mechanically ventilated subjects. Enrolment will continue in both the **body** mg MEDI3902 and placebo groups while the PK interim analysis is conducted. If the mean serum concentration of MEDI3902 on Day 22 in the **body** mg MEDI3902 dose group is lower than the target concentration of **body** µg/mL, a dose adjustment to **body** mg MEDI3902 will be considered. An independent DMC will be responsible for recommending dose adjustment.

In case of a dose adjustment from **Seed** mg to **Rede** mg MEDI3902, approximately 143 subjects will be randomised to receive the **Rede** mg MEDI3902 dose to maintain 1:1 ratio with the placebo group. Subjects who have been enrolled and randomised in the mg and **Rede** mg MEDI3902 groups will be followed until the end of the study period (Day 50).

[figure not shown]
Jac

# ledacted

Subjects will be followed through Day

50 (49 days post investigational product administration Figure 3.1.1-1).

The study is being conducted through the Innovative Medicines Initiative Joint Undertaking (IMI JU, 2012), which is a pan-European public-private partnership between the European Commission and the European Federation of Pharmaceutical Industries and Associations. The Sponsor will execute this study in conjunction with Combatting Bacterial Resistance in Europe - Molecules against Gram Negative Infections (COMBACTE-MAGNET), which is a consortium of partners from the pharmaceutical industry and academia in the field of antibiotic-resistant bacteria, hospital-acquired pneumonia and ventilator-associated pneumonia.

↓ Post-dose follow-up

#### Figure 3.1.1-1 Study Flow Diagram

ADA = anti-drug antibody; IV = intravenous; N = number of subjects; PK = pharmacokinetics

a In case of a dose adjustment from Red mg to Red mg MEDI3902, approximately 143 subjects will be randomised to receive the 3000 mg MEDI3902 dose to maintain 1:1 ratio with the placebo group. Subjects who have been enrolled in the Red mg and Red mg MEDI3902 groups will be followed until the end of the study period (Day 50).

Note: This study flow diagram was revised based on the change in the study design and illustrates how approximately 286 subjects will be randomised in a 1:1 ratio to one of the two treatment groups: revealing MEDI3902 (or revealing mg in case of dose adjustment; N = 143) or placebo (N = 143). Efficacy will be assessed through 21 days postdose (Day 22); safety, PK and ADA will be assessed through 49 days postdose (Day 50). The sample size may be modified after approximately 50% of the subjects are enrolled and followed through 21 days postdose based on blinded assessment of the event rate and/or attrition rate in the overall population.

The endpoints to be measured in this study are described in Section 2.2.

# 3.1.2 Treatment Regimen

At study start, subjects were to be randomly assigned to receive a single dose of Red mg MEDI3902, Red mg MEDI3902, or placebo administered via IV infusion on Day 1. However, based on emerging data (see Section 3.1.1), subsequent to Amendment 2, subjects will be enrolled and randomly assigned (1:1 ratio) to receive a single IV infusion of

mg MEDI3902 (or in the case of dose adjustment, Reda mg MEDI3902) or placebo.

# 3.1.3 Management of Study Medication Related Toxicities

All subjects will be premedicated with antihistamine, for example, and mg diphenhydramine IV, clemastine mg IV, or dexchlorpheniramine mg IV (or another antihistamine preparation utilised in routine clinical practice for management of acute allergic reactions) within 15 to 30 minutes prior to start of IP administration. The data monitoring committee (DMC) will monitor the rate and severity of infusion or allergic reactions observed during the study. The DMC may authorise additional premedication of subjects with acetaminophen mg orally and/or methylprednisolone mg IV in combination with the antihistamine, or the antihistamine together with famotidine mg orally with or without acetaminophen and/or methylprednisolone prior to start of investigational product infusion.

In the event of any infusion related reactions observed, the following options should be considered:

- 1. Administer antihistamine, for example, diphenhydramine mg IV, clemastine mg IV, or dexchlorpheniramine mg IV, or another antihistamine preparation utilised in routine clinical practice for management of acute allergic reactions.
- 2. Administer methylprednisolone Re mg IV
- 3. Stop the infusion, and reassess the signs and symptoms as well as the overall condition of the patient in about 30 to 60 minutes
  - a. If the signs and symptoms abate, consider restarting the study drug at an infusion rate, approximately half of the baseline infusion rate
  - b. If the signs and symptoms of infusion related reaction do not show resolution, or there is worsening of the symptoms or in subject's general condition, permanently discontinue the study drug, and consider additional symptomatic treatment, including but not limited to antihistamines, epinephrine, and or systemic corticosteroids

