# 4.1.6 Discontinuation of Investigational Product

All randomised subjects will receive a single dose of investigational product. An individual subject will not receive investigational product if any of the following occur in the subject in question:

- 1. Withdrawal of consent
- 2. An AE that, in the opinion of the investigator or the sponsor, contraindicates dosing
- 3. Subject is determined to have met one or more of the exclusion criteria or failed to meet all of the inclusion criteria for study participation
- 4. A severe or potentially life-threatening serious systemic, allergic, or local reaction with onset after dosing has been initiated. If such a reaction is observed during investigational product infusion, the infusion would be immediately stopped, no further investigational product will be administered and the medical monitor must be contacted immediately.

Subjects who have not received investigational product, regardless of reason, will not be followed and collection of AEs will not be performed. Unless consent for follow-up is withdrawn, subjects discontinued after receiving a partial dose of investigational product will be followed for the full study period (through 49 days postdose) with all laboratory and clinical evaluations collected as defined in the protocol.

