# 5.3.2 Hypersensitivity (Including Anaphylaxis) and Infusion related Reactions

Administration of polyclonal immunoglobulin preparations and mAbs have been associated with hypersensitivity (including anaphylaxis) and infusion related reactions that occur during or after dosing. A hypersensitivity reaction is defined as an acute onset of an illness with involvement of the skin, mucosal tissue, or both, during infusion of investigational product (but does not meet the definition of anaphylaxis). Anaphylaxis is an acute onset, potentially fatal, systemic allergic reaction that is distinct from simple allergic reactions (eg, rash, pruritus) because of the simultaneous involvement of several organ systems (Sampson et al, 2006). An infusion related reaction is defined as any other reaction (other than hypersensitivity or anaphylaxis) occurring during infusion of investigational product or felt to be temporally related to the infusion.

Anaphylaxis and infusion related reactions have some common manifestations and may be difficult to distinguish from each other. Infusion related reactions typically develop within

30 minutes to 2 hours after the initiation of first drug infusion. However, though less frequent, infusion related reactions can occur later on within first 24 hours from the start of infusion, and are less common following subsequent exposures. Infusion related reactions may manifest with single or multiple signs and symptoms. Most of them are mild in intensity, but severe and even fatal reactions have been reported. Unlike infusion related reaction, anaphylaxis is a rare event, usually occurring after subsequent exposure to antigen, and it is most commonly accompanied by severe systemic skin and/or mucosal reactions. A full definition of anaphylaxis is provided in Appendix 3.

Signs and symptoms of hypersensitivity (including anaphylaxis) and infusion related reactions include, but are not limited to, fever, chills, rigors, myalgia, weakness, flushing, sweating, headache, dizziness, lightheadedness, syncope, seizure, anxiety, nasal congestion, rhinitis, sneezing, oropharyngeal or laryngeal edema, bronchospasm, dyspnea, tachypnea, cyanosis, respiratory arrest, tachycardia, hypotension, arrhythmia, chest pain, ischemia or infarction, cardiac arrest, flushing, erythema, pruritus, urticaria, angioedema, maculopapular rash, nausea, vomiting, cramping, and diarrhea (Kang and Saif, 2007).

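### Protocol 3.1.3 and 4.1.6 item 4 both cover a severe, serious infusion related reaction that abates, and neither section says which governs stopping and restarting

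*Protocol*

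**What the plan says.** Protocol 3.1.3 introduces its guidance with "In the event of any infusion related reactions observed, the following options should be considered". The options are an antihistamine, methylprednisolone, and stopping the infusion with reassessment after about 30 to 60 minutes. Under the stopping option: "If the signs and symptoms abate, consider restarting the study drug at an infusion rate, approximately half of the baseline infusion rate". If the reaction does not resolve, or the symptoms or the subject's general condition worsen, the drug is permanently discontinued. The section sets no threshold for severity at onset and does not mention the medical monitor.

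Protocol 4.1.6 opens its list with "An individual subject will not receive investigational product if any of the following occur in the subject in question". Item 4 on that list is "A severe or potentially life-threatening serious systemic, allergic, or local reaction with onset after dosing has been initiated". If such a reaction is seen during the infusion, "the infusion would be immediately stopped, no further investigational product will be administered and the medical monitor must be contacted immediately". Nothing is said about a reaction that later abates.

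Protocol 5.3.2 supplies the definitions. Hypersensitivity is a separate class: "A hypersensitivity reaction is defined as an acute onset of an illness with involvement of the skin, mucosal tissue, or both, during infusion". Infusion related reactions are the residual class: "An infusion related reaction is defined as any other reaction (other than hypersensitivity or anaphylaxis) occurring during infusion of investigational product". On their severity it says: "Most of them are mild in intensity, but severe and even fatal reactions have been reported".

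**The concern.** The two sections address the same bedside event in different terms. An investigator working from 3.1.3 could treat the stop as discretionary, or consider a restart once the subject improves, in a case where 4.1.6 bars further product. Sites could then handle the same reaction differently, and some would breach 4.1.6 without realising it. About 120 sites were planned at study start.

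The first thing at stake is the safety of a subject who has just had a severe reaction. The second is the consistency of the descriptive data, because whether an infusion ends or resumes determines what is recorded as a discontinuation, an interruption or a partial dose.

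**Working it through.** No arithmetic applies. The check compares the two scopes, sorts reactions into cases, and looks for text elsewhere that ranks the sections.

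**Scopes.** Section 3.1.3 reaches every infusion related reaction. Section 4.1.6 item 4 reaches reactions that are severe or potentially life-threatening and also serious, whether systemic, allergic or local, with onset after dosing has begun. Section 5.3.2 defines infusion related reactions by what they are not (hypersensitivity or anaphylaxis) and by timing, not by severity. It also says that severe ones have been reported. The two scopes therefore intersect.

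**Cases among infusion related reactions during infusion.**

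1. The reaction does not meet item 4. Only 3.1.3 applies, and there is no conflict.
2. The reaction meets item 4 and does not resolve, or worsens. Both sections end treatment, so they agree on further product. They differ on the stop itself, which is an option in 3.1.3 and mandatory in 4.1.6.
3. The reaction meets item 4 and abates. Section 3.1.3 lets a restart be considered; 4.1.6 allows no further product. They differ on the stop and on what follows it.

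The difference over restarting is confined to case 3. The difference over stopping covers cases 2 and 3.

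**Text that might settle it.** Neither section refers to the other. Section 4.7.2.1 sends the reader to 3.1.3 for medications to use in an infusion reaction and does not mention 4.1.6. The sections on monitoring of dosing (4.5.1.3), on anaphylaxis and infusion related reactions (5.3.2) and on immediate reporting (5.6.4.1) contain no stop or restart rule that ranks the two. SAP 3.4.3 tabulates infusion interruptions but does not say which reactions may be restarted.

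**Where it would show in the analysis.**

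- Adverse events leading to discontinuation (SAP 3.8.3).
- Dose intensity and interruptions (SAP 3.4.3).
- Possibly serum PK summaries, through partial rather than full doses (SAP 3.10).
- Possibly the table of AESI duration (SAP 3.8.2).

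Membership of the mITT and As-treated populations does not change, because any amount of product qualifies a subject (Protocol 4.8.1, Analysis Populations).

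**The case against.** The strongest reply is that the sections can be obeyed together. Section 3.1.3 only offers options and never requires a restart, while 4.1.6 is mandatory and more specific. An investigator who stops at once, gives no more product and calls the medical monitor complies with both. Read as a general permission limited by a specific prohibition, the protocol gives one answer, and what is missing is a cross-reference. Most of this stands, and it is why the point is a clarification rather than a flat contradiction. It remains an inference that the reader has to draw. Section 3.1.3 has its own trigger for permanent discontinuation, so it can be read as complete.

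Controls also exist. The DMC monitors the rate and severity of infusion reactions (3.1.3), vital signs are taken every 30 minutes during infusion (4.5.1.3), and infusion related reactions reach the sponsor within 24 hours (5.6.4.1). These limit undetected divergence between sites, but they do not tell the investigator which section applies.

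A reader might infer that the sections conflict for all infusion related reactions, or for anaphylaxis and hypersensitivity. The documents do not support this. Most infusion related reactions are described as mild and fall only under 3.1.3. Section 5.3.2 defines the other two as separate classes, although it concedes that anaphylaxis and infusion related reactions can be hard to tell apart.

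A reader might also want to name one reaction, such as isolated bronchospasm, as certain to fall under both sections. That cannot be secured. The Section 5.2 example of a serious bronchospasm concerns treatment in an emergency room or at home, not in an intubated ICU patient, and Appendix 2 warns that a Grade 3 event need not be serious.

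**Conclusion.** The point holds as a narrow ambiguity in a safety rule, of low severity. A reaction that meets 4.1.6 item 4, is an infusion related reaction under 5.3.2 and then abates is covered by two sections with different instructions. Precedence is suggested by the wording of 4.1.6 but not stated.

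Its size cannot be given. The readable documents contain no frequency for such reactions, and the remark in 5.3.2 about severe and fatal cases is background on antibody products, not a rate in this trial. Since most reactions are described as mild, the number affected is probably small and could be zero.

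A reader might infer a threat to the primary efficacy result. The documents do not support that: partially dosed subjects stay in the mITT population, and with few subjects involved any effect is likely negligible, though it cannot be shown to be exactly nil.

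The conclusion rests on two assumptions. The requirement that the reaction be serious is read as applying to all reactions in item 4; if it applied only to the life-threatening ones, the overlap would be wider. No blacked-out text is assumed to rank the sections; the gaps in 3.1.3 appear to be drug doses only.

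**What to change.** The sponsor should reconcile 3.1.3 with 4.1.6 item 4 so that an infusion related reaction meeting item 4 has one consistent instruction on stopping, restarting and contacting the medical monitor. Section 3.1.3 should state which reactions its stop and restart options cover, and the two sections should refer to each other. The choice of rule is clinical and belongs to the sponsor's safety physician; this review takes no position on it.

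The cost is a protocol clarification and a memo to sites. Sample size and statistical methods are unaffected.
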